Section 5.2, Inclusion Criteria, Inclusion criterion 5.	
Original text:
 
 Men who are sexually active with a woman of childbearing potential and have not had a vasectomy must agree to use a barrier method of birth control e.g., either condom or partner with occlusive cap (diaphragm or cervical/vault caps) with spermicidal foam/gel/film/cream/suppository for the duration of the study plus 3 months after receiving the last dose of study drug, and all men must not donate sperm during the study and for 3 months after receiving the last dose of study drug. In addition, their female partners should also use an additional method of birth control (which may include a hormonal method, an intrauterine device [IUD] or an intrauterine system [IUS]) for at least the same duration. 
Changed into:
 
 Men who are sexually active with a woman of childbearing potential and have not had a vasectomy must agree to use a barrier method of birth control i.e., a condom with spermicidal foam/gel/film/cream/suppository for the duration of the study plus 3 months after receiving the last dose of study drug, and all men must not donate sperm during the study and for 3 months after receiving 	Based on Amendment GER-1: Men with WOCBP partners should use a barrier method of birth control (condom) in every case.

Section number and Name	Description of Change	Brief Rationale
	the last dose of study drug. In addition, their female partners should also use an additional method of birth control (which may include a hormonal method, an intrauterine device [IUD] or an intrauterine system [IUS]) for at least the same duration.	
Section 5.2, Inclusion Criteria, inclusion criterion 6.1.	
Original text:
 
Not of childbearing potential: postmenopausal (>45 years of age with amenorrhea for at least 12 months, or any age with amenorrhea for at least 6 months and a serum follicle stimulating hormone (FSH) level at screening >40 IU/L without hormonal replacement therapy); permanently sterilized (e.g., tubal occlusion [tubal cauterization and other comparable methods], hysterectomy, bilateral salpingectomy); or otherwise be incapable of pregnancy.
 
Changed into:
 
Not of childbearing potential defined as:
 
 Postmenopausal (amenorrhea for at least 12 months without an alternative medical cause. A serum follicle stimulating hormone (FSH) level at screening >40 IU/L in women not using hormonal contraception or hormonal replacement therapy may be used for confirmation, however in the absence of 12 months of amenorrhea, a single FSH measurement is insufficient) or Permanently sterilized (including hysterectomy, bilateral salpingectomy and bilateral oophorectomy) or Otherwise be incapable of pregnancy. 	Based on Amendment GBR-1.
Section 5.3, Exclusion Criteria, Exclusion criterion 13.	
Original text:
 
Subject has a history of hepatitis B surface antigen (HBsAg) or hepatitis C antibody (anti-HCV) positive, or other clinically active liver disease, or tests positive for HBsAg or anti-HCV at Screening. If subjects have been successfully treated for HCV and are RNA negative, they will be allowed in the study.
 
Changed into:
 
Subject has a history of hepatitis B surface antigen (HBsAg) or hepatitis C antibody (anti-HCV) positive, or other clinically active liver disease, or tests positive for HBsAg or anti-HCV at Screening. If subjects have been successfully treated for or have been spontaneously recovered from HCV and are RNA negative, they will be allowed in the study.
	Some subjects recover spontaneously from HCV without any treatment. These subjects have a positive antibody test but a negative RNA-test.
Section 5.3, Exclusion Criteria, Exclusion criterion 16.	
Original text:
 
Subject has positive test result(s) for alcohol or drugs of abuse (including barbiturates, methadone, opiates, cocaine, cannabinoids,
	As benzodiazepines may be allowed under certain conditions, a positive urine drug screen on

Section number and Name	Description of Change	Brief Rationale
	
amphetamine/methamphetamine, benzodiazepines and ecstasy) at Screening or at baseline (Visit 2).
 
Subjects with a positive alcohol or drug screen may have the test repeated once, based on the investigator's discretion. This determination, and the reason for permitting a repeat test, must be recorded in the subject's source documents and initialed by the investigator. A positive, repeat alcohol or drug screen is exclusionary.
 
Changed into:
 
Subject has positive test result(s) for alcohol or drugs of abuse (including barbiturates, methadone, opiates, cocaine, cannabinoids, amphetamine/methamphetamine, and ecstasy) at Screening or at baseline (Visit 2).
 
A positive test result for benzodiazepines is not exclusionary if the subject is taking such drugs per protocol.
 
Subjects with a positive alcohol or drug screen may have the test repeated once, based on the investigator's discretion. This determination, and the reason for permitting a repeat test, must be recorded in the subject's source documents and initialed by the investigator. A positive, repeat alcohol or drug screen is exclusionary.
	benzodiazepines is not always exclusionary.
Section 5.3, Exclusion Criteria, Exclusion criterion 25.	
Original text:
 
 Has known allergies, hypersensitivity, or intolerance or any contraindication to JNJ-67953964 (refer to IB for JNJ-67953964). 
Changed into:
 
 Has known allergies, hypersensitivity, or intolerance or any contraindication to any of the excipients of JNJ-67953964 or placebo (refer to IB for JNJ-67953964). 	Based on Amendment GER-1: To exclude subjects with an allergy, hypersensitivity, intolerance or any contraindication to the use of placebo
Section 7.3, Participant Discontinuation/Withdrawal from the Study	
Original text:
 
 Subjects who drop out will be replaced if the number of subjects completing the study will be below 96. Replacement subjects will receive a new subject ID-number and will be assigned to a new randomization code in the IWRS. 
Changed into:
 
 Subjects who drop out, other than for safety reasons related to the study drug or study procedures, will be replaced if the number of subjects completing the study will be below 96. A maximum of 32 subjects (1/3 of targeted subjects) will be allowed to be 	Based on Amendment GER-1: To define a maximum number of replacement subjects. In addition, only those subjects will be replaced which have not withdrawn due to adverse drug reactions or adverse events based on study procedures.

Section number and Name	Description of Change	Brief Rationale
	replaced. Replacement subjects will receive a new subject ID-number and will be assigned to a new randomization code in the IWRS.	
Section 7.3, Participant Discontinuation/Withdrawal from the Study	
The text in section 7.3 will be changed from:
 
A subject will be discontinued from the study if the QTcF interval is higher than 500 msec or is prolonged >60 msec from the baseline value. Similarly, subjects presenting with a first-degree bundle branch block (BBB; PR > 200 msec) will be discontinued. QTc interval prolongation and BBB should be confirmed by collecting 2 additional ECGs as soon as possible after the initial ECG. The average value of the QTcF interval of the three ECG's will be used to determine whether a subject should be discontinued. If the QTcF is not readily available, the QTcB may be used instead. The subject will continue to be monitored (maximum 12 hours) by repeated 12 lead ECGs (at least every 60 minutes) until the ECG normalizes.
 
To
 
A subject will be discontinued from the study if the QTcF interval is higher than 500 msec or is prolonged >60 msec from the baseline value. QTc interval prolongation should be confirmed by collecting 2 additional ECGs as soon as possible after the initial ECG. The average value of the QTcF interval of the three ECG's will be used to determine whether a subject should be discontinued. If the QTcF is not readily available, the QTcB may be used instead. The subject will continue to be monitored (maximum 12 hours) by repeated 12 lead ECGs (at least every 60 minutes) until the ECG normalizes.
	
A withdrawal criterion for the PR-interval (> 200 msec) has been included which is conflicting with inclusion criterion 3 (subject with PR-interval >220 are excluded).
 
This withdrawal criterion on the PR-interval will be removed from Section 7.3. The rationale for this removal is
 
 • Subjects with a PR-interval ≥ 220 msec are already excluded from the study per inclusion criterion 3. • The PR-interval does not increase under the influence of any medicinal product.
Section 8.5.1, Time Period and Frequency for Collecting Adverse Event and Serious Adverse Event Information	
Original Text:
 
 • All SAEs occurring during the study must be reported to the appropriate sponsor contact person by study-site within 24 hours after their knowledge of the event. 
Changed into:
 
 • All SAEs occurring during the study must be reported to the appropriate sponsor contact person by study-site personnel immediately, without undue delay, under no circumstances later than 24 hours after their knowledge of the event. 	Based on Amendment GER-1: To adjust the wording of the timeframe for reporting SAEs in line with the German law (Section 12 para 4 GCP ordinance) and European rules (2011/C 172/01/EC, „CT-3“, 4.3.1, 29.).
Section 10.11, Appendix 11	Added: Past x years = Past 1 year	Correction of omission
Protocol amendments	Correct date of Amendment INT-2 to 26 February 2019	This date was not consistent in Amendment INT-2.

Amendment INT-2 (26-February-2019)

Overall Rationale for the Amendment: Administrative change to add the EudraCT number because of additional trial execution in the EU, changes of inclusion criterion on female sterilization, exclusion criteria on concomitant medication due to reconsideration of current clinical practices and some changes on request of clinical sites.

Section number and Name	Description of Change	Brief Rationale
Section 5.3, Exclusion Criteria, exclusion criterion 5.	
Has failed (no more than 25% response on ATRQ) three or more antidepressant treatments including the current SSRI/SNRI and including the current and all previous depressive episodes despite an adequate dose (per ATRQ) and duration (at least 6 weeks).
 
Changes into:
 
Has failed (no more than 25% response on ATRQ) three or more antidepressant treatments including the current SSRI/SNRI during the current depressive episode despite an adequate dose (per ATRQ) and duration (at least 6 weeks).
	To align better to the current clinical practice. Obtaining data from previous episodes is complex in clinical practice.
Section 5.3, Exclusion Criteria, exclusion criterion 17.	
Original text:
 
 • Antipsychotic drugs (D₂-antagonists) within 2 weeks before screening. 
Changed into:
 
 • Antipsychotic drugs (D₂-antagonists) within 2 weeks before screening. However, Seroquel (quetiapine) in a dose ≤ 100 mg is allowed when used in a stable dose for at least 8 weeks prior to screening. Quetiapine treatment should be continued unchanged during the study. 	Low dose quetiapine and trazodone are used as a sedative drug during treatment of depression. The effect on depression itself when used in a stable low dose is limited
Section 5.3, exclusion criterion 18.	
Original text:
 
 • benzodiazepines. 
Changed into:
 
 • Benzodiazepines when used only as needed (PRN) is not allowed. A subject may continue to take a benzodiazepine treatment only if: 
 • The subject has been taking a stable daily dose for at least 6 weeks prior to screening • The dose does not exceed an equivalent of 2 mg of lorazepam per day. • Allowed benzodiazepines are lorazepam (≤ 2 mg/day), clonazepam (≤ 0.5 mg/day) and alprazolam (≤ 1 mg/day) being taken daily. Other benzodiazepines should be discussed before subject enrollment with the study responsible physician. • Treatment will be continued unchanged during the study. 	Benzodiazepines in stable use have limited effects on current depression and anxiety severity levels.

Section number and Name	Description of Change	Brief Rationale
Section 6.5 Concomitant medication	
Original text:
 
 benzodiazepines. 
Changed into:
 
 Benzodiazepines when used only as needed (PRN) is not allowed. A subject may continue to take a benzodiazepine treatment only if: 
 The subject has been taking a stable daily dose for at least 6 weeks prior to screening The dose does not exceed an equivalent of 2 mg of lorazepam per day. Allowed benzodiazepines are lorazepam (≤ 2 mg/day), clonazepam (≤ 0.5 mg/day) and alprazolam (≤ 1 mg/day). Other benzodiazepines should be discussed before subject enrollment with the study responsible physician. Treatment will be continued unchanged during the study. 	Benzodiazepines in stable use have limited effects on current depression and anxiety severity levels.
Section 6.5 Concomitant medication	
Original text:
 
 Antipsychotic drug (D₂-antagonists), lithium and other mood stabilizers from 2 weeks before screening. 
Changed into:
 
 Antipsychotic drugs (D₂-antagonists) within 2 weeks before screening. However, Seroquel (quetiapine) in a dose ≤ 100 mg is allowed when used in a stable dose for at least 8 weeks prior to screening. Quetiapine treatment should be continued unchanged during the study. Trazodone for treatment of insomnia in a dose ≤ 100 mg when used for at least 8 weeks at a stable dose will be allowed. 	Low dose quetiapine and trazodone are used as a sedative drug during treatment of depression. The effect on depression itself when used in a stable low dose is limited
Section 2.3 and references.	Update: Investigator brochure is now edition 3, January 2019	
Section 4.1 Overall design	Added “audio” to recording	specification
Section 5.2 Inclusion criteria, inclusion criterion 6 first bullet point	Added: tubal cauterization and other surgical interruption of the fallopian tubes as an allowed means for female sterilization.	Update on current medical practice.
Section 5.4 Lifestyle considerations. No 3.	Added units of alcohol (UK standards)	On request of UK-based sites
Section 8.2.3 Double-blind treatment period	Added: At their last study visit, each study participant will be invited to complete an IEC/IRB approved Experience Survey, to share his/her experience as a volunteer in this study. The responses will be collected by an external party and anonymously provided to the sponsor.	Was missing in previous version.

Section number and Name	Description of Change	Brief Rationale
Section 8.3.1, Rater Qualification	This section about the rater qualification and training process has been added.	Policy to optimize rater training.
Section 10.2	
 • Follicle stimulating hormone (FSH) 
Changed into
 
 • For postmenopausal women only: Follicle stimulating hormone (FSH) 	To limit unnecessary testing
Section 1.2 Time and Events schedule	
Added: meals during study visits.
 
Download and install Q.16 app
 
Changed into
 
Download and install app(s) at screening and baseline.
	Missing elements in previous version of protocol.

Amendment INT-1 (18-June-2018)

This amendment is considered to be substantial based on the criteria set forth in Article 10(a) of Directive 2001/20/EC of the European Parliament and the Council of the European Union.

Overall Rationale for the Amendment: To harmonize with procedures of some vendors, to update dosing instructions and to correct some typo's.

Section number and Name	Description of Change	Brief Rationale
Section 5.3, Exclusion Criteria, exclusion criterion 5.	
Original text:
 
5. Has failed (no more than 20% response) three or more antidepressant treatments with a different pharmacological mode of action including the current SSRI/SNRI despite an adequate dose (per ATRQ) and duration (at least 6 weeks) during a previous or the current depressive episode.
 
Changed into:
 
1. Has failed (no more than 25% response on ATRQ) three or more antidepressant treatments including the current SSRI/SNRI and including the current and all previous depressive episodes despite an adequate dose (per ATRQ) and duration (at least 6 weeks).
	
The ATRQ form uses ≤25% as the lowest response criterion. The exclusion criterion is now harmonized with the ATRQ.
 
To harmonize the study procedures with those of the independent reviewers and to prevent that too many 'unrecognized therapy resistant subjects' will be randomized in the study, the wording "with a different pharmacological mode of action" has been removed.

Section 5.3, exclusion criterion 17.	
Original text:
 
 • Proton pump inhibitors within 2 weeks before screening. 
Changed into:
 
 • Proton pump inhibitors within 4 weeks before screening. 	Typo, was inconsistent with exclusion criterion 3.
Time and Events Schedule (TES); PROTOCOL SUMMARY, Sections 4.1, 6.1	
Remove "morning" from several sections.
 
Time and Events schedule, footnote "d":
 
Original text: At home: In the morning in fasting condition. At clinic visit days: In fasting condition after completion of
	Study medication should be taken after 4-hours fasting. This is preferably done in the morning. However, medication may also be taken before lunch and

Section number and Name	Description of Change	Brief Rationale
and 8.2.2.	
predose assessments.
 
Changed into: At home: In fasting condition. At clinic visit days: Use blisters dispensed at the previous visit. In fasting condition after completion of predose assessments.
 
Section 4.1 and summary:
 
Original text:
 
The first dose will be taken at home next morning on Day 2.
 
Changed into:
 
The first dose will be taken at home on Day 2.
 
Section 6.1 and summary:
 
Original text:
 
All subjects will take 2 capsules QD. The capsules will be taken daily from Day 2 to Day 78 every morning (at home and when being in the clinic) in fasting condition with some water (fasting for at least 4 hours before dosing; water intake is permitted during that period).
 
The subjects will take the study medication with them at each study visit and will take study medication at the site in fasting condition after completion of predose study assessments and blood collections. Dosing will be witnessed by the study staff.
 
Changed into:
 
All subjects will take 2 capsules QD. The capsules will be taken daily from Day 2 to Day 78 (at home and when being in the clinic) in fasting condition with some water (fasting for at least 4 hours before dosing; water intake is permitted during that period). Study medication will be taken before breakfast. If the subject has forgotten to take the study medication before breakfast, this should be done before the next following meal, at the latest at dinner of the same day. If the subject remembers later than dinner, the dose of that day should be omitted, and the subject should take his dose before breakfast on the next day.
 
The subjects will take the study medication with them at each study visit and will take study medication - from the blisters dispensed at the previous study visit - at the site in fasting condition after completion of predose study assessments and blood collections. Dosing will be witnessed by the study staff.
	
before dinner. Because of the long $t_{1/2}$ of the study drug, drug intake may be up to 12 hours after the planned dosing time.
 
Additionally, during a study visit, study drug from the blisters dispensed at the previous visit should be dosed.

Section 6.4	
Original text:
 
Dosing will be documented by an app using the subjects' smartphone.
	
To add specific information about the AiCure-app to record compliance of drug intake.

Section number and Name	Description of Change	Brief Rationale
	
Changed into:
 
Dosing will be documented by app's using the subjects' smartphone, or on a smartphone provided to the subject if they are unable to use their own. The Q1.6-app will present an electronic diary asking subjects to confirm dosing of study medication. When available, also a medication adherence monitoring platform (AiCure®-app) will be used. The Platform uses artificial intelligence on smartphones to visually confirm proper medication administration and ingestion of the study drug in real time without human intervention. Video recordings of the drug intake are also recorded and stored to AiCure's secure server for further analysis to reconfirm proper medication administration, to identify any usability issues or intentional non-adherence, and to check for duplicate enrollment. In addition, built-in reminders and a communication system allow real-time intervention by study personnel in case of improper drug administration or interruptions by the subject.
	
Section 8.1	
Added:
 
 Manuals for investigator and subject for the AiCure-app to assess treatment compliance by video recording the drug intake. The AiCure-app will be downloaded on the subjects' own smartphone, or a smartphone with the app included will be provided to the subject. 	To inform about additional materials supplied for AiCure-app
Section 8.2.1	
Original text:
 
As duplicate enrollment and protocol violations are risk factors for poor quality data and safety concerns, each subject in this study must have their current study status checked by a clinical trials verification system. This is a mandatory process.
 
Changed into:
 
As duplicate enrollment and protocol violations are risk factors for poor quality data and safety concerns, each subject in this study will have their current study status checked by a clinical trials verification system when available.
	The verification system may not be available for this study due to new privacy regulations in the EU. As a global company, Janssen has determined that the requirements of the EU privacy regulations will be followed for all studies even in cases where no study sites are located in the EU.

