In study G, the AE's that showed an incidence greater than 5% and were at least double that observed in the placebo group were pruritus, anxiety, rash, constipation, tinnitus, blurred vision, abnormal coordination, disturbance in attention, postural dizziness, non-cardiac chest pain and dysuria.

No SAEs have been reported from any of the clinical studies.

Based on safety data from the 3 Phase 1 clinical studies and the studies D to G, no potential risks related to JNJ-67953964 administration have been identified. Only a limited number of AEs observed in the single-dose and multi-dose PK studies, Study LAFA and Study LAFB, were considered by the investigator to be related to JNJ-67953964. Additionally, there were no clinically significant changes in vital signs or ECGs in the studies.

An update of safety data from ongoing studies will be presented in the IB or addenda to the IB.

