6. Subject has received an investigational drug (including investigational vaccines) or used an invasive investigational medical device within 3 months before the planned first dose of

^a This section has been amended by amendment INT-1, INT-2 and INT-3

study drug, or has participated in any interventional clinical studies on MDD in the previous 1 year, or is currently enrolled in an interventional study.

7. Has signs or symptoms of Cushing's Disease, Addison's Disease, primary amenorrhea, or other evidence of significant medical disorders of the HPA axis.
8. Is breast feeding.
9. Subject has a history of malignancy within 5 years before screening (exceptions are squamous and basal cell carcinomas of the skin and carcinoma in situ of the cervix, or malignancy that in the opinion of the investigator, with concurrence with the sponsor's study responsible physician, is considered cured with minimal risk of recurrence).
10. Has one or more of the following diagnoses:

- A primary DSM (5th edition) diagnosis of:
 - GAD
 - panic disorder
 - obsessive compulsive disorder (OCD)
 - posttraumatic stress disorder (PTSD)
- Subjects with comorbid GAD, SAD, or panic disorder for whom MDD is considered the primary diagnosis are not excluded.
- A current diagnosis or diagnosis in the past 1 year of:
 - psychotic disorder
 - MDD with psychosis
 - anorexia nervosa or bulimia nervosa.
 - chronic fatigue syndrome
 - bipolar disorder (BD)
 - mental retardation
 - antisocial or borderline personality disorder
 - autism spectrum disorder.

11. Has a current or recent history of clinically significant suicidal ideation within the past 6 months, corresponding to a score of 4 (active suicidal ideation with some intent to act, without specific plan) or 5 (active suicidal ideation with specific plan and intent) for ideation on the C-SSRS, or a history of suicidal behavior within the past 1 year, as validated by the C-SSRS at screening or Visit 2. Subjects with a prior suicide attempt of any sort, or prior serious suicidal ideation/plan > 6 months ago, should be carefully screened for current suicidal ideation and only included at the discretion of the investigator.

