 - Continuous use of zolpidem, zopiclone, eszopiclone and ramelteon. Note: Nonbenzodiazepines sleep aids (including: zolpidem, zaleplon, and eszopiclone) are allowed on an as needed (PRN) basis during the study but NOT within 24 hours before being in the clinic and not more than 2 nights in a row.
 - S-adenosyl methionine (SAMe)
 - Melatonin, agomelatine
- NSAIDs and aspirin.

19. Is unwilling or unable to undergo multiple venipunctures because of poor tolerability or lack of easy access.

20. Is unable to read and understand the ICF and PRO, complete study-related procedures, and/or communicate with the study staff.

21. Subject has any condition for which, in the opinion of the investigator, participation would not be in the best interest of the subject (e.g., compromise the well-being) or that could prevent, limit, or confound the protocol-specified assessments.

22. Subject has had major surgery, (e.g., requiring local or general anesthesia) within 12 weeks before screening, or will not have fully recovered from surgery, or has surgery planned during the time the subject is expected to participate in the study.

23. Is a vulnerable subject (e.g., a person kept in detention).

24. Has received any prior treatment with electroconvulsive therapy, vagal nerve stimulation, or a deep brain stimulation device or treatment with ketamine or esketamine for MDD.

25. Criterion modified by Amendment INT-3.

- 25.1. Has known allergies, hypersensitivity, or intolerance or any contraindication to any of the excipients of JNJ-67953964 or placebo (refer to IB for JNJ-67953964).
26. Has either donated 1 or more units (approximately 450 mL) of blood or acutely lost an equivalent amount of blood within 60 days before the first dose of study drug.
27. Has cognitive impairment that would render the informed consent invalid or limit the ability of the subject to comply with the study requirements.
28. Subject is an employee of the investigator or study site, with direct involvement in the proposed study or other studies under the direction of that investigator or study site, as well as family members of the employees or the investigator.

NOTE: Investigators should ensure that all study enrollment criteria have been met at screening. If a subject's status changes (including laboratory results) after screening but before first dose of study drug is given such that they now meet an exclusion criterion, they should be excluded from participation in the study.

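### Exclusion criterion 25.1 no longer names JNJ-67953964 itself, and the amendment that changed it does not explain why

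*Protocol*

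**What the plan says.** The operative text is Protocol Section 5.3, criterion 25.1. It excludes a person who "Has known allergies, hypersensitivity, or intolerance or any contraindication to any of the excipients of JNJ-67953964 or placebo", followed by a pointer to the Investigator's Brochure.

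The INT-3 entry in the Protocol Amendment Summary of Changes shows what this replaced. The superseded criterion read "Has known allergies, hypersensitivity, or intolerance or any contraindication to JNJ-67953964 (refer to IB for JNJ-67953964". The replacement text in that entry is the same as the current 25.1. The rationale column attributes the change to the German local amendment, GER-1, and gives one purpose: "To exclude subjects with an allergy, hypersensitivity, intolerance or any contraindication to the use of placebo".

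Two other criteria in Section 5.3 bear on the point. Criterion 6 applies where "Subject has received an investigational drug (including investigational vaccines) or used an invasive investigational medical device within 3 months before the planned first dose", or where the person "has participated in any interventional clinical studies on MDD in the previous 1 year", or is currently enrolled in an interventional study. Criterion 21 is the general discretionary rule: "Subject has any condition for which, in the opinion of the investigator, participation would not be in the best interest of the subject".

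**The concern.** An exclusion for people who have reacted to the investigational product, or for whom it is contraindicated, would normally name the active substance. Here it did until INT-3. The edit changed the object of the criterion from the drug to its excipients, while the reason given concerns placebo only. Read literally, a person with a documented reaction to JNJ-67953964 does not meet 25.1.

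The stake is individual safety at enrolment, and consistency between sites. One investigator may apply 25.1 as written, and another may assume that the drug is still covered. The lost cover is also wider than former participants. The criterion speaks of contraindication as well as allergy, and a contraindication does not require earlier exposure.

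**Working it through.** No figure in the plan depends on this criterion, so there is nothing to recompute. The check is textual.

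**1. Is the issue in the current protocol or only in the change log?** A difference between a log and current text would not be an error. Here the INT-3 replacement text and the operative 25.1 agree, so the wording is live.

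**2. What does the criterion cover?**

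| Text | Object of the exclusion |
|---|---|
| Before INT-3 | JNJ-67953964 |
| Stated aim of INT-3 | placebo |
| Current 25.1, reading A: excipients of (JNJ-67953964 or placebo) | excipients of the active capsule; excipients of placebo |
| Current 25.1, reading B: (excipients of JNJ-67953964) or placebo | excipients of the active capsule; placebo |

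The phrase is ambiguous, but neither reading contains the active substance. Adding the stated aim to the pre-INT-3 object would have given drug plus placebo. The text instead gives excipients plus placebo (or its excipients).

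**3. Is the removal explained?** No. When INT-3 removed something on purpose it said so: the entry for Section 7.3 states that the PR-interval withdrawal rule is removed and gives two reasons. The entry for criterion 25 has nothing comparable.

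**4. Does another criterion name the drug?** Reading through Section 5.3, criteria 1 to 28:
- Criterion 6 works by time since investigational treatment (3 months) or since an interventional MDD study (1 year), or by current enrolment. It does not ask about a reaction.
- Criterion 21 depends on the investigator's opinion and does not mention reactions to study drug.
- No criterion bars earlier exposure to this compound.

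**5. Would the criterion 6 windows catch former participants anyway?** Study G, the mood and anxiety disorder study, is the closest population. Section 2.3, last amended by INT-2 (26 February 2019), already reports its recruitment as complete, and treatment lasted 8 weeks. Assume that the last recruit started dosing on 26 February 2019. Then:
- last dose: 26 February + 56 days = 23 April 2019;
- end of the 3-month window: about 23 July 2019;
- date of INT-3: 28 August 2019.

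On that assumption the 3-month window had lapsed for all of Study G when INT-3 took effect. The 1-year window would still have applied to the later participants if Study G counts as an interventional MDD study, which the protocol does not say. Criterion 6 therefore narrows the gap and does not close it.

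**The case against.** The strongest reply is that such a person is very unlikely to be enrolled. A known reaction to the study drug fits criterion 21 squarely. Section 5.1 tells investigators to take questions about eligibility to the study responsible physician. The pointer to the Investigator's Brochure remains in 25.1, and Section 7.3 allows withdrawal for safety or tolerability. All of this stands and limits the practical impact. None of it puts the drug back into the criterion: discretion and a cross-reference are weaker than a named exclusion, and withdrawal acts only after dosing.

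Intent also cannot be settled. The change came from GER-1, whose own text is not in the documents. The most that can be said is that the stated rationale does not account for the loss of the active substance.

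Four stronger readings are tempting, and the documents do not support them.
- *That INT-3 did the opposite of what it set out to do.* It set out to cover placebo, and it does. The loss of the drug is an unexplained side effect.
- *That a large exposed pool is at risk.* Stated exposures can be added: 73 (Phase 1) + 70 (Study D) + 62 (Study E) + 13 (Study F completers) + 45 (Study G) = 263. But 73 + 40 = 113 of these were healthy subjects, 23 in Study D were cocaine-dependent in early abstinence, and Studies E and F enrolled smokers. Only Study G resembles this trial's population. Its active arm is given as 45 (Protocol Section 2.3), about 44 (Protocol Section 4.3) or 43 (SAP Section 1), and those with a known reaction would be a fraction of that.
- *That Study G demonstrates hypersensitivity.* Protocol Section 2.2.2 says that the events above 5% and at least double placebo "were pruritus, anxiety, rash, constipation, tinnitus, blurred vision" and others. It does not describe them as allergic, and it reports no serious adverse events in any clinical study.
- *That the blind is threatened.* Anyone previously exposed might recognise the drug, with or without a reaction. Rewording 25.1 would not change that.

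**Conclusion.** The point holds as a drafting gap in a live eligibility rule. Criterion 25.1 does not name the active substance on either reading, the stated rationale does not explain the omission, and no other numbered criterion names it.

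Its size is small. The number of people affected is not given and is assumed to be none to a few of about 142. There is no consequence for the estimand, sample size, power, type I error or any analysis. It is worth correcting because the consequence, though improbable, falls on an individual subject's safety.

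The conclusion rests on the literal wording of Section 5.3 and the INT-3 entry. It would change only if GER-1 or the Investigator's Brochure, neither of which is available here, showed that the active substance was left out deliberately and is covered elsewhere.

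**What to change.** The sponsor should check GER-1 for the reason behind the change and reconcile 25.1 with both its stated rationale and its pre-INT-3 wording. The criterion should then state explicitly whether it covers the active substance as well as the excipients and placebo, in a form that also removes the two-way reading of the phrase. If the omission was unintended, this means restoring the sponsor's own earlier object, JNJ-67953964, alongside the INT-3 addition; no new clinical rule is needed. If it was intended, the rationale should say so and say where the drug itself is dealt with. The eligibility checklist should be updated to match.

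Cost: one line in the next amendment and one on the checklist. No extra visit, test or subject.
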